6. STUDY OBJECTIVES

6.1 Primary Objective

The primary objective of this study is to evaluate the neutralization of the IFN gene signature following treatment with IFN-K, as measured by the change from baseline of the expression of IFN-induced genes **and** to evaluate the efficacy of treatment with IFN-K using the British Isles Lupus Assessment Group (BILAG)-based Composite Lupus Assessment (BICLA) response criteria. The study will be considered as positive if a statistically significant better effect of IFN-K compared to placebo is observed on the neutralization of the IFN gene signature and if at least a trend favoring IFN-K is observed on the BICLA response.

6.2 Secondary Objectives

The secondary objectives of this study are:

- To evaluate the efficacy of treatment with IFN-K using:
 - The SLE Responder Index [(SRI)-4 and above]
 - The SLE Disease Activity Index-2000 index (SLEDAI-2K)

- The BILAG-2004 index
- The Safety of Estrogen in Lupus Erythematosus National Assessment-SLEDAI (SELENA-SLEDAI) Flare index
- The Systemic Lupus International Collaborating Clinics/American College of Rheumatology Damage Index for Systemic Lupus Erythematosus (SLICC/ACR-DI)
- The Cutaneous Lupus Erythematosus Disease Area and Severity Index (CLASI) in patients with cutaneous lesions at baseline
- To evaluate the immune response induced by IFN-K:
 - Anti-IFN α antibody response
 - Anti-IFN α antibody neutralizing capacities
 - Anti-KLH antibody response
- To assess the safety of IFN-K emulsified with ISA 51 VG

6.3 Exploratory Objectives

The exploratory objectives of this study are:

- To assess disease activity using:
 - The Physician Global Assessment (PGA) score
 - The 28-Tender and Swollen joint counts
 - A Joint Pain Visual Analog Scale (VAS)
 - The flare description
 - The changes in Lupus therapy
- To assess quality-of-life using:
 - The Short Form-36 (SF-36) questionnaire
 - The Functional Assessment of Chronic Illness Therapy (FACIT) fatigue score.
- To assess biological parameters:
 - Levels of lupus-related serum auto-antibodies and biomarkers
 - Neutralizing Anti-IFN α antibodies towards IFN α subtypes
 - Anti-IFN α and anti-KLH antibody isotyping
 - IFN β cross neutralization

- Antibody response to influenza vaccination
- To assess correlations between immune responses, IFN gene signature and clinical responses

7. INVESTIGATIONAL PLAN

This will be a Phase IIb, randomized, double-blind, placebo-controlled, multicenter study assessing intramuscular (IM) administration of IFN-K against a adjuvanted placebo. Study patients will be enrolled into one of two treatment groups and allocated in 1:1 randomization ratio to receive the study product: IFN-K or placebo as outlined below:

- Group 1: IFN-K emulsified in ISA 51 VG
- Group 2: placebo emulsified in ISA 51 VG

The study will consist in a main study followed by an Extended Follow up Period.

During the main study, each patient will receive two injections of study product (corresponding to 240 mcg of IFN-K or placebo) at three visits during the Induction Period (at Week 0 [Visit 2], Week 1 [Visit 3], and Week 4 [Visit 4]). Each patient will be administered one injection of study product (corresponding to 120 mcg of IFN-K or placebo) during the Maintenance Period (at Week 12 [Visit 6] and Week 24 [Visit 9]).

The main study comprises a total of 12 visits occurring over a period of 40 weeks. The study will be divided into four periods: a 4-week Screening Period that will be performed to determine eligibility of the patients for randomization into the study, a 12-week Induction Period, a 12-week Maintenance Period and a 12-week Follow-up Period.

The Extended Follow up Period applies to all patients who have completed the main study. Then, when the results of the main study are available, only patients who have received IFN-K will continue the Extended Follow-up Period for up to 60 months (240 weeks) after Visit 12 (Week 36).

7.1 Screening Period (from Study Week -4 to 0)

Patient eligibility will be determined over the course of the Screening Period.

In order to determine their eligibility, candidate participants will undergo a series of assessments and procedures as outlined in Table 1 and in Section 10.9.1. All relevant samples should be collected before any new SLE related treatment is initiated.

Randomization will be minimized according to the criteria described in Section 9.2.2.

7.2 Induction Period (Week 0 to Week 12)

When screening results are available and should all entry criteria be fulfilled, the patients will be allocated to receive IFN-K or a placebo, according to a 1:1 randomization ratio, and enter the 12-week Induction Period during which each patient will receive three administrations of study product on Visit 2 (Week 0), Visit 3 (Week 1), and Visit 4 (Week 4).

The patients will undergo planned assessments and procedures as outlined in Table 1 and in Sections 10.9.2 to 10.9.6.

Note that Visit 6 (Week 12) is the last visit of the Induction Period and the first visit of the Maintenance Period.

7.3 Maintenance Period (Week 12 to Week 24)

Following the Induction Period, patients will be followed during the 12-week Maintenance Period.

During the Maintenance Period, patients will undergo planned assessments and procedures as outlined in Table 1 and in Sections 10.9.6 to 10.9.9.

A booster dose will be administered at Visit 6 (Week 12) and at Visit 9 (Week 24).

Visit 9 (Week 24) is the last visit of the Maintenance Period and the first visit of the Follow-up Period.

7.4 Follow-up Period (Week 24 to Week 36)

Following the Maintenance Period, patients will be followed during the 12-week Follow-up Period.

During the Follow-up Period, patients will undergo planned assessments and procedures outlined in Table 1 and sections 10.9.9 to 10.9.12.

Patients will not receive any study treatment during this period.

7.5 Extended Follow-up Period (Week 36 to Week 276)

All patients who have completed the Follow-up Period before un-blinding of treatment arm is performed will enter into an extended follow up period for up to 60 months (240 weeks) after Visit 12 (Week 36). Then, when the study results are available, only patients who have received IFN-K will be followed for up to 60 months.

Patient will not receive any study treatment during this period.

During this extended follow up period, the patients will be followed every 6 months for 5 years and will undergo planned assessments and procedures as outlined in Table 1 and section 10.9.14.

The visit at Week 276 (Month 69) (FU10 Visit) will be considered as the last planned visit.

If patients remain positive for anti-IFN α neutralizing antibodies after this Extended Follow up Period, they will be proposed to be enrolled in another 5-year follow up study to confirm the favorable safety profile of IFN-K.

7.6 Planned Analyses

The primary analysis will be performed at Week 36.

A follow-up analysis will be performed at year 5 (week 276 - Month 69) when all patients have completed the extended follow up. For safety purpose, a descriptive analysis will be performed at regular intervals, according to Development Safety Update Report (DSUR) timelines.

8. STUDY POPULATION

8.1 Number of Patients

The target number of eligible patients to be enrolled in this study is 178 (89 patients in each treatment group).

8.2 Recruitment Method

This study will be performed in multiple centers worldwide. There will be competitive recruitment.

8.3 Eligibility Criteria

Patients will need to meet the following eligibility criteria at study entry to be eligible for this study.

8.3.1 Inclusion criteria

A patient meeting all of the following inclusion criteria at screening will be eligible for participation in this study:

1. Has had a diagnosis of SLE according to current ACR criteria (4 of 11 ACR criteria) (list of criteria provided in Appendix 1)

2. Has SLEDAI ≥ 6
3. Has at least 1 BILAG A and/or at least 2 BILAG B
4. Has a positive IFN gene signature by RT-qPCR as assessed on a limited number of genes
5. Has anti-nuclear antibodies (ANA) $\geq 1:160$ and/or anti-dsDNA antibodies ≥ 7.0 IU/mL
6. Be a male or female, aged between 18 and 65 years, inclusive, at the time of the screening visit
7. Agrees to receive influenza vaccination during each influenza season of the study period
8. Currently receiving at least one of the following treatment:
 - Corticosteroids (CS) at a dose of ≤ 20 mg of prednisone equivalent/day
 - Antimalarial drugs (hydroxychloroquine [HCQ] or chloroquine [CQ]); the patient must have been treated since at least 8 weeks and on stable dose for at least 4 weeks prior to first planned administration of the study product
 - Methotrexate (MTX); the patient must have been treated and be on stable dose (≤ 20 mg/week) for at least 12 weeks prior to the first planned administration of the study product
 - Azathioprine (AZA); the patient must have been treated and be on stable dose (≤ 2.5 mg/kg/day) for at least 12 weeks prior to the first planned administration of the study product
 - Mycophenolate mofetil (MMF), the patient must have been treated and be on stable dose (≤ 2 g/day) for at least 12 weeks prior to the first planned administration of the study product
9. Study patient and his/her partner has to use effective method of contraception for the duration of the study including the Extended Follow up Period.

Note: If of child bearing potential, effective contraception methods include:

- Female sterilization (have had surgical bilateral oophorectomy with or without hysterectomy) or tubal ligation at least 6 weeks prior to the first planned administration of the study product. In case of oophorectomy alone, the reproductive status of the woman must be confirmed by follow up hormone level assessment.
- Male sterilization (at least 6 months prior to Screening).
- Combination of the following:
 - Oral, injected or implanted hormonal methods of contraception or other forms of hormonal contraception that have comparable efficacy (failure rate $<1\%$), for example hormone vaginal ring or transdermal hormone contraception **or**
 - Placement of an intrauterine device (IUD) or intrauterine system (IUS)
 - **And** barrier methods of contraception: condom or occlusive cap (diaphragm or cervical/vault caps) with spermicidal foam/gel/film/cream/vaginal suppository

Women are considered post-menopausal and not of child bearing potential if they have had 12 months of natural (spontaneous) amenorrhea with an appropriate clinical profile (e.g. age appropriate, history of vasomotor symptoms) or have had surgical bilateral oophorectomy (with or without hysterectomy) or tubal ligation at least six weeks ago. In

the case of oophorectomy alone, she is considered not of child bearing potential only when the reproductive status of the woman has been confirmed by follow up hormone level assessment.

10. Is able and willing to comply with the requirements of the study protocol (e.g., completion of the diary cards, return for follow-up visits), in the opinion of the Investigator
11. Has provided written informed consent

8.3.2 Exclusion criteria

A patient meeting any of the following exclusion criteria at study entry will not be eligible for the study:

1. Has active, severe lupus nephritis as defined either by the immediate need for cyclophosphamide treatment or by renal BILAG A
2. Has active, severe, neuropsychiatric SLE, defined as neuropsychiatric BILAG A
3. During the 4 months prior to the first planned study product administration, has been treated with corticosteroids (CS) at a dose of >20 mg of prednisone equivalent/day for > 7 consecutive days
4. Is currently receiving or has received pulse dose CS (\geq 250 mg prednisone equivalent/day) within 3 months prior to the first planned administration of the study product.
5. Has received potent immunosuppressive drugs such as cyclophosphamide, cyclosporine A, oral tacrolimus within 3 months prior to the first planned administration of the study product
6. Has received abatacept, sifalimumab, rontalizumab, anifrolumab, belimumab, TNF antagonists or another registered or investigational biological therapy within 6 months prior to the first planned administration of the study product
7. Has received anti-B-cell therapy (e.g., rituximab, epratuzumab) within 12 months prior to the first planned administration of the study product
8. Has significant electrocardiogram (ECG) abnormalities that are clinically relevant and preclude study eligibility in the Investigator's opinion
9. Has inflammatory joint or skin disease other than SLE that may interfere with study assessments
10. Has any laboratory abnormality other than SLE related that is clinically relevant and precludes study entry in the Investigator's opinion.
11. Has a history of malignant cancer, except the following treated cancers: cervical carcinoma in situ, basal cell carcinoma, or dermatological squamous cell carcinoma.

For US patients only: Has a history of malignant cancer, except the following treated cancer: basal cell carcinoma. Note: only patients with negative screening tests for malignancy according to The American Cancer Society guidelines (see Appendix 12), documented within the 12 months prior screening visit will be enrolled.

12. Has frequent recurrences of oral or genital herpes simplex lesions (≥ 6 occurrences during the 12 months prior to first study product administration)
13. Has had an episode of shingles during the 12 months prior to the first planned administration of the study product
14. Has no IgG against herpes simplex virus (HSV-1 and HSV-2), varicella zoster virus (VZV), cytomegalovirus (CMV) or Epstein-Barr virus (EBV)
15. Is positive for HTLV 1-2 antibodies, HIV antibodies, Hepatitis C (HCV) antibodies, or Hepatitis B surface antigen (HBsAg)
16. Is at high risk of significant infection and/or has any current signs or symptoms of infection at entry or has received intravenous antibiotics within 2 months prior to the first planned administration of the study product
17. Has received any live vaccine within 3 months prior to the first planned administration of the study product (e.g. nasal flu vaccine, oral poliomyelitis vaccine, measles-mumps-rubella vaccine, yellow fever vaccine, Japanese encephalitis vaccine, dengue vaccine, rotavirus vaccine, varicella vaccine, zoster vaccine, Bacillus Calmette-Guérin [BCG] vaccine, oral typhoid vaccine)
18. Has used any investigational or non-registered product within 30 days or 5 half-lives, whichever is longer, or any investigational or non-registered vaccine within 30 days prior to the first planned administration of the study product
19. Has a history of chronic alcohol and/or drug abuse within 6 months prior to the first planned administration of the study product
20. Is breastfeeding, pregnant, or planning to become pregnant during the study period
21. Has known hypersensitivity to any component of the study product
22. Is high-risk human papilloma virus (HPV) positive by reverse transcription polymerase chain reaction (RT-qPCR) on a cervical swab at Screening or within 3 months prior to the first planned study product administration
23. Has cytological abnormalities \geq HSIL (High Grade squamous intraepithelial lesions) on a cervical swab at Screening or within 3 months prior to the first planned study product administration

9. INVESTIGATIONAL PRODUCT AND ADMINISTRATION

9.1 Study Products

The IFN-K study product has been developed by Neovacs SA. and manufactured by a designated contract manufacturing organization (CMO) in compliance with current Good Manufacturing Practice (GMP) requirements and guidelines for injectable products.

All study materials required for the study product preparation and administration will be supplied by Neovacs SA and are listed in Table 2.

IFN-K is provided as a liquid formulation in single-use vials to be emulsified with ISA 51 VG, as described in Section 9.1.3.

IFN-K is a conjugated immunotherapeutic agent. It is a complex between rhu-IFN α 2b and KLH subunit obtained by conjugation with glutaraldehyde and subsequent inactivation/stabilization with formaldehyde and glycine treatment. The formulation is a sterile clear solution for injection. Each DIN 2R vial contains at least 150 mcg of IFN-K in a volume of 0.4 mL of phosphate buffer.

ISA 51 VG is the oil-based adjuvant Montanide® ISA 51 VG. It is a sterile clear yellow liquid composed of Montanide® 80 VG, a non-ionic surfactant of plant origin in highly purified mineral oil Drakeol® 6VR. Each DIN 2R vial contains 3.0 mL ISA 51 VG.

Placebo is provided as an ampoule of 2 mL of sterile sodium chloride solution (0.9% NaCl) to be emulsified with ISA 51 VG as adjuvant.

Note: Refer to the current version of the IB for further information about study products and their components.

Table 2 Study Products and Materials

Study product	Formulation/Vial	Presentation	Volume
IFN-K	At least 150 mcg of IFN α conjugated with KLH (IFN-K)	Solution for injection in single-use vial to be emulsified with ISA 51 VG	0.4 mL (DIN 2R vials)
Placebo	0.9% Sodium Chloride solution	Solution for injection in single-use vial to be emulsified with ISA 51 VG	2 mL (ampoule)
Adjuvant	Montanide® ISA 51 VG	Liquid formulation	3 mL (DIN 2R vials)
Ancillaries		Syringes, syringe caps, needles, connector with filter	

IFN-K = Interferon-kinoid; KLH = Keyhole limpet hemocyanin.

9.1.1 Packaging and Labelling

All clinical trial packaging and labelling operations will be performed according to current GMP. The contents of the label will be in accordance with all applicable regulatory requirements specified by each country participating in the trial.

Each treatment kit will be identified by a unique treatment number and will consists of:

- two vials of IFN-K or one ampoule of placebo,
- one vial of ISA 51 VG,
- two syringes, two syringe caps, one connector and four needles.

9.1.2 Kit Storage, Preparation, and Return

The study products and the materials will be supplied to the Investigational site packed in one kit with appropriate vials and outer-packaging labels and an “Instructions for use” leaflet.

The study product should be stored under refrigerated conditions at (+2 - +8°C).

When kits are received at the site, Pharmacist or authorized designee shall check for accurate delivery, ensure that the study product is in good condition, verify that it arrived within the specified temperature ranges and place it in a refrigerator (+2 - +8°C) as soon as possible.

Study kits will be stored away from light in a securely locked area that is accessible only to authorized personnel until they are administered to the patients. The site will maintain a temperature log to ensure that study kits are stored within the correct temperature range. They should be removed from the refrigerator at least 1 hour before preparation. The emulsion ideally will be prepared extemporaneously, immediately prior to use.

The unblinded study pharmacist or authorized designee will prepare each dose of IFN-K or placebo and provide the syringe(s) containing the emulsion to the Investigator. The same standard procedure for the emulsion preparation will be used for all doses. It will be communicated to each Investigational site in the provided Pharmacy Manual. Briefly, the procedure for one emulsion preparation comprises the following steps:

The volume of the 2 vials of IFN-K is transferred in a 2 mL syringe. The same volume of adjuvant is loaded into a second syringe. Both syringes must be attached to the connector after clearing as much air as possible from the system.

The emulsion process takes place in two steps:

- Emulsion starts by transferring alternatively the formulation from one syringe to the other very slowly.
- After the first 20 cycles performed slowly over 2 minutes, the speed is increased for 40 additional cycles performed in less than 50 seconds. When the emulsion starts to form, resistance will be felt and the mixture develops as a creamy viscous appearance. For the Placebo, 0.8 mL of 0.9% NaCl solution is transferred in a 2 mL syringe. Then, the emulsion process is the same as described above for IFN K emulsion.

After completion of the preparation, the total volume emulsion should be equally distributed with an equivalent volume of IFN-K (or placebo) in each syringe, each corresponding to an ultimate IFN-K dose of 120 mcg. The two syringes should then be disconnected from the connector and a sterile needle for IM administration or syringe cap should be attached to each syringe. The prepared syringes will be labelled with the study number, the subject number and the date and time of reconstitution/preparation of the study treatment. Labels prepared for IFN-K and placebo doses will be identical to ensure blind procedures.

The Pharmacist or authorized designee will maintain study products accountability and the return to Neovacs SA of unused test materials. This will include receipt, preparation, return dates, quantities, batch numbers, product name, vial numbers and the numbers of the vials allocated to the patients. The Pharmacist or authorized designee will maintain records that adequately document that the patients were provided with the dose specified by the protocol and reconcile all investigational products received from Neovacs SA. After completion of the study, all unused study products will be returned to designated CMO, unless otherwise requested by Neovacs SA in writing.

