Investigational Therapy:	
The study product IFN-K has been developed by Neovacs SA.
 
All study materials, prepared in compliance with current Good Manufacturing Practice (GMP) requirements and guidelines for injectable products, will be provided by Neovacs SA.
 
The investigational therapy is composed of IFN-K/placebo emulsified in ISA-51 VG to be administered by intramuscular injection.
 
IFN-K is a conjugated immunotherapeutic agent. It is a complex between recombinant human (rhu)-IFNα2b and KLH subunit obtained by conjugation with glutaraldehyde and subsequent inactivation/stabilization with formaldehyde and glycine treatment. It is then formulated as a solution for injection in phosphate buffer.
 
Placebo is a sterile physiological saline solution (0.9% NaCl).
 
ISA 51 VG is the oil-based adjuvant Montanide[®] ISA 51 VG. It is a sterile clear yellow liquid composed of Montanide[®] 80 VG, a non-ionic surfactant of plant origin in highly purified mineral oil Drakeol[®] 6VR.
 
Two vials of IFN-K are emulsified in ISA 51 VG to obtain a dose of 240 mcg in a volume of 1.2 mL. The volume of study product to be injected will be adapted to the dose to be administered.
 
One ampoule of placebo will be prepared and injected in the same way.

Treatment Duration:	
Each patient will receive a dose of 240 mcg of IFN-K/placebo (1.2 mL of study product administered in two injections) at 3 visits during the Induction Period (at Week 0 [Visit 2], Week 1 [Visit 3], and Week 4 [Visit 4]).
 
Each patient will be administered a dose of 120 mcg of IFN-K/placebo (0.6 mL of study product administered in one injection) at 2 visits during the Maintenance Period (at Week 12 [Visit 6] and Week 24 [Visit 9]). The

	
duration of the intermittent study treatment will be 24 weeks from the first (Week 0 [visit 2]) to the last administration (Week 24 [visit 9]).

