5.2.5 Safety analyses

Safety variables will be tabulated and presented for all patients included in the Safety population (SAF).

5.2.5.1 ***Extent of exposure and compliance***

Compliance (see section 9) with study treatment will be presented by treatment group on the FAS and the PP populations. Treatment compliance will then be analyzed as a numerical variable as well as a categorical variable (Statistical table 14.1.28, Listing 16.2.5.1).

Statistical Analysis Plan

Study Name: IFN-K-002

SAP version & date: v4, 18/Jun/2018

To analyze the extent of exposure the following variables will be summarized by treatment group for the SAF (Statistical table 14.3.1, Listing 16.2.5.2):

- Number of administrations received and cumulative dose
- Duration (number of days) between first IP application and last IP application.
- Presence of anti-IFN α neutralizing antibodies

All administration of study product data will be provided in Listing 16.2.5.3.

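### Vial content, mixing instruction and injected volumes do not consistently define the dose: whole syringes hold at least 300/150 mcg before losses, the synopsis volumes at least 225/112.5 mcg, against a stated 240/120 mcg

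*Protocol*

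**What the plan says.** **Content.** Protocol Section 9.1: "Each DIN 2R vial contains at least 150 mcg of IFN-K in a volume of 0.4 mL of phosphate buffer". Table 2 repeats the content as a minimum. No nominal content or upper limit is given. Section 9.1.1 puts in each kit "two vials of IFN-K or one ampoule of placebo".

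**Mixing.** Section 9.1.2: "The volume of the 2 vials of IFN-K is transferred in a 2 mL syringe". Then: "The same volume of adjuvant is loaded into a second syringe". Section 5.4.1 confirms the 1:1 ratio by volume. The placebo instruction confirms the starting volume: "For the Placebo, 0.8 mL of 0.9% NaCl solution is transferred in a 2 mL syringe".

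**Division.** Section 9.1.2 then shares the total emulsion equally between the two syringes, "each corresponding to an ultimate IFN-K dose of 120 mcg". It names no volume to inject or discard.

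**Injected volume.** The synopsis (Investigational Therapy) says: "Two vials of IFN-K are emulsified in ISA 51 VG to obtain a dose of 240 mcg in a volume of 1.2 mL". Under Treatment Duration it gives 1.2 mL in two injections for the 240 mcg visits and 0.6 mL in one injection for the 120 mcg visits. It adds that the injected volume is adapted to the dose. Section 9.1.3 and Table 3 give doses without volumes. The visit lists in Section 10.9 say only two syringes (Visits 2, 3 and 4) or one syringe (Visits 6 and 9).

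**Analysis.** SAP Section 5.2.5.1 summarises "Number of administrations received and cumulative dose". SAP Section 9 defines compliance as amount taken over amount prescribed, with category limits at 80% and 120%.

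**The concern.** The protocol describes one preparation in two places, and the two descriptions imply different amounts. A reader who follows Section 9.1.2 and the visit lists literally would inject the full contents of each syringe. A reader who follows the synopsis would inject a smaller volume of the same emulsion.

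Dose is the exposure under test. Section 5.5 bases dose selection on 240 and 120 mcg, and 240 mcg is the highest dose level reported from the Phase I-II study (Section 5.4.3). Before losses, the literal Section 9.1.2 reading lies above that level. Section 9.1.2 also asks the pharmacist for records showing that patients received the protocol's dose, which presupposes that the protocol fixes it. The SAP's cumulative dose is only as meaningful as the amount attached to each administration.

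**Working it through.** **Inputs.** Content per vial *c*, at least 150 mcg in 0.4 mL (Section 9.1); two vials per preparation (9.1.1, 9.1.2); adjuvant equal in volume to the IFN-K solution (9.1.2). Stated doses are 240 mcg in 1.2 mL and 120 mcg in 0.6 mL (synopsis), with three full doses and two boosters.

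**Stated concentration.** 240/1.2 = 200 mcg/mL and 120/0.6 = 200 mcg/mL. The synopsis is consistent with itself.

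**Emulsion made under Section 9.1.2.**
- IFN-K solution: 2 × 0.4 = 0.8 mL, matching the placebo volume.
- Emulsion: 0.8 + 0.8 = 1.6 mL, not 1.2 mL.
- Content: 2 × 150 = 300 mcg or more.
- Concentration: 300/1.6 = 187.5 mcg/mL or more.

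**Reading A, synopsis volumes.** At the minimum content, 1.2 × 187.5 = 225 mcg and 0.6 × 187.5 = 112.5 mcg. For exactly 240 mcg, *c* = 200 × 1.6/2 = 160 mcg per vial, which a minimum of 150 allows.

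**Reading B, whole syringes, no loss.** Each syringe is 1.6/2 = 0.8 mL and holds 150 mcg or more; two hold 300 mcg or more. For exactly 240 mcg, *c* = 240/2 = 120 mcg per vial, which a minimum of 150 excludes.

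| | Full dose | Booster | Course (3 full + 2 boosters) |
|---|---|---|---|
| Stated | 240 mcg | 120 mcg | 3 × 240 + 2 × 120 = 960 mcg |
| A, at *c* = 150 | 225 mcg | 112.5 mcg | 3 × 225 + 2 × 112.5 = 900 mcg |
| B, at *c* = 150 | 300 mcg | 150 mcg | 3 × 300 + 2 × 150 = 1200 mcg |
| A, at *c* = 160 | 240 mcg | 120 mcg | 960 mcg |
| B, at *c* = 160 | 320 mcg | 160 mcg | 3 × 320 + 2 × 160 = 1280 mcg |

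The rows at *c* = 150 are lower bounds, since no upper limit is stated. At that floor, A is 225/240 − 1 = −6.25% and B is 300/240 − 1 = +25% relative to the stated dose. The ratio B/A is 1.6/1.2 = 1.33 for any *c*.

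**Losses.** The documents give no loss figure. Losing emulsion reduces volume but not concentration. At *c* = 150, a loss of 1 − 240/300 = 20% leaves 240 mcg, but in 240/187.5 = 1.28 mL. A loss of 0.4 mL leaves 1.2 mL, but 225 mcg. At *c* = 160, a loss of 0.4 mL leaves 1.2 mL holding 240 mcg. So loss can make every passage agree, but only with a vial content and a loss that are both unstated.

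**The case against.** The strongest reply is that the passages describe overfill or recovered volume. Drawing up two vials, clearing air, 60 transfer cycles of a viscous emulsion and a connector with a filter all cost material. If about 1.2 mL is recovered from vials holding 160 mcg, half is 0.6 mL and 120 mcg, and injecting the whole syringe gives the stated dose. Alternatively, 0.8 mL per syringe may be intended with 0.6 mL injected. The synopsis remark about adapting the volume to the dose fits that, although it equally fits two syringes versus one. Section 9.1.2 presents its steps as a summary and refers to a Pharmacy Manual, which may state the volume.

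Much of this stands, and it rules out three stronger readings:
- **A reader might infer that the stated figures cannot give 240/120 mcg at all.** They can: the vial content is a minimum, and 160 mcg satisfies it. On the synopsis volumes the dose is undetermined, not contradicted.
- **A reader might infer that patients were given too much, or that sites gave different doses.** Nothing shows this. One standard procedure is meant for every dose, and the Manual has not been seen.
- **A reader might infer that the SAP's compliance figures are wrong.** The SAP does not say whether amounts are nominal or measured. If nominal amounts are used throughout, any common scaling cancels and compliance would not reveal it. If delivered amounts were set against nominal ones, reading B would give at least 300/240 = 125%, beyond the 120% limit.

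Nor does an offset common to the IFN-K arm bias the randomised comparison. It affects the dose to which the result is attributed. What the reply does not supply is any statement in the protocol of the loss, the surplus or the volume injected per syringe in the sections that govern preparation and administration.

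**Conclusion.** The protocol does not consistently define its own dose. Before losses, injecting both equally divided syringes is incompatible with 240 mcg, and injecting one is incompatible with 120 mcg: they hold at least 300 and 150 mcg. Injecting 1.2 or 0.6 mL delivers at least 225 or 112.5 mcg and equals the stated dose only at 160 mcg per vial. The two readings differ by one third whatever the vial content.

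This rests on complete withdrawal of both vials, a uniform emulsion and, for the whole-syringe figures, no preparation loss. The arithmetic is certain on those assumptions. Which reading sites followed is unknown, because the Pharmacy Manual is not available. The point warrants correction because it bears on exposure and safety and is cheap to settle. No view is taken on which dose or volume is right.

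**What to change.** Reconcile the synopsis (Investigational Therapy and Treatment Duration), Section 9.1 with Table 2, and Section 9.1.2 with each other and with the Pharmacy Manual. Vial content, emulsion volume, injected volume per syringe and handling of any surplus should agree with the stated dose. Carry the injected volume into Sections 9.1.2 and 9.1.3 and Table 3. The sponsor decides which figures stand.

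If dosing is complete, establish the amounts actually delivered from the pharmacy and batch records that Section 9.1.2 already requires, and report them with the SAP's cumulative dose.

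The cost is wording in the protocol and Pharmacy Manual or, after dosing, a records check and a short addition to the exposure report. It needs no extra patients, visits or procedures.
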